Clinical Investigation Plan

CP327

Randomized clinical trial assessing the effect of transanal irrigation with cone catheter versus conservative bowel management on symptoms of low anterior resection syndrome after rectal resection

January 2020- Maj 2021

21st of January 2020

Study Sponsor / Data Controller: Coloplast A/S

[name]

[name]

Denmark

NCT04586634

SYNOPSIS OF THE CLINICAL INVESTIGATION

Synopsis of the clinical investigation

Objective

The primary objective is to demonstrate superiority of the Peristeen cone catheter compared to standard of care.

The secondary objective is to investigate quality of life and different benefits and aspects of treatment and satisfaction with the Peristeen cone catheter.

Design of the investigation

This is a randomised, open-label, parallel investigation comparing the Peristeen cone catheter with standard of care in subjects with major LARS (LARS score ≥ 30). Each subject will be enrolled for a study duration of 12 weeks. Subjects will be randomized to the treatments stratified by neo-adjuvant radiotherapy.

The comparator in this study will be current standard of care for patients with LARS which is conservative bowel management. This is defined as: Supportive therapy according to the individual treatment protocols available at each participating site.

Primary endpoint and secondary endpoints

Primary endpoint:

- LARS score, obtained from the LARS score questionnaire*

Secondary endpoints:

- Number of subjects with Major LARS*
- FIQL Score – scale 1, Modified American Society for Colorectal Surgeons Questionnaire*
- FIQL Score – scale 2, Modified American Society for Colorectal Surgeons Questionnaire*
- FIQL Score – scale 3, Modified American Society for Colorectal Surgeons Questionnaire*
- FIQL Score – scale 4, Modified American Society for Colorectal Surgeons Questionnaire*
- EQ-5D-5L – utility score*
- EQ-5D-5L – VAS score (scale 0-10 cm)*
- Satisfaction with treatment (scale 0-10 cm)*
- Number of adverse events*

*All endpoints are measured per subject at study termination

Exploratory endpoints:

A horizontal line of text that has been completely redacted with black ink, leaving only a thin white space where the text once was.

*All endpoints are measured per subject at study termination

9. Postoperative radiotherapy for rectal cancer	Can potentially affect LARS
10. Underlying diarrhoeal disease	Can potentially affect LARS
11. Neurologic disease assessed to be a significant contributory cause to LARS symptoms	Can potentially affect LARS
12. Former or current use of transanal irrigation	Patients to be naïve to transanal irrigation
13. Participating in other interventional clinical investigations	Can potentially affect LARS

Investigational devices and comparator

The Peristeen transanal irrigation system is a manual system consisting of a control unit (featuring a pneumatic bulb pump and a four-position rotary switch), a water bag (featuring a pressure relief valve), a cone catheter, tubes and connectors. The system is also accompanied by straps to secure the system on the thigh while being used, if needed, and a toilet bag to store the system in when not in use. Peristeen is a non-sterile product classified as class I device according to the Medical Device Directive, MDD 93/42/EEC and is CE-marked.

The comparator in this investigation is current standard of care for patients with LARS which is conservative bowel management.

Investigation approval

The investigation will be approved by the Ethical Committee in France and notified to French ANSM and French Data Protection Body (named CNIL) when receiving the EC approval, before the investigation can be initiated.

Assessment(s)						
On-site visit						

 • LARS score Questionnaire • FIQL score Questionnaire • EQ – 5D – 5L • Satisfaction with treatment • [REDACTED] • [REDACTED] 	Subject/Investigator (All)		X			X
On-site visit						X

 • [REDACTED] • [REDACTED] 	Subject/Investigator (Peristeen Cone only)					
Subject diary:						

 • [REDACTED] • [REDACTED] • [REDACTED] 	Subject (All) Run-in period (14 days from Visit 1)		X	X		
Subject diary:				X		

 • [REDACTED] 	Subject (Peristeen Cone only)					
Device training	Investigator		X			
AE/SAE reporting			X		X	X
Registration of termination						
Termination form	Investigator					X

> TABLE OF CONTENTS

1. List of personnel involved in the Investigation	12
1.1. Sponsor representatives	12
1.2. Investigator.....	12
2. Rational/justification for conducting the clinical investigation	12
3. Objective of the clinical investigation	13
3.1. Objective.....	13
4. Investigational device and comparator(s)	13
4.1. Description of investigational device	13
4.1.1. Manufacturing	14
4.2. Identification and traceability of the device	14

The newly developed and CE-marked device Peristeen Cone catheter has been designed to be better suited for patients with specific clinical and anatomical considerations such as LARS patients in view of their post-surgical bowel anatomy. Furthermore, due to sphincter-sparing surgical techniques, the majority of LARS patients have an acceptable sphincter function and good hand dexterity, thus limiting the need for a self-supported inflatable balloon catheter.

The current standard of care for patients with LARS is conservative bowel management. This is defined as supportive therapy according to the individual treatment protocols available at the site. However, many patients continue to suffer from LARS symptoms despite the conservative bowel management. The objective of the study is therefore to demonstrate that the Peristeen system with Cone Catheter is superior compared to standard of care for patients with LARS symptoms.

3. Objective of the clinical investigation

3.1. Objective

The primary objective is to demonstrate superiority of the Peristeen cone catheter compared to standard of care.

The secondary objective is to investigate quality of life and different benefits and aspects of treatment and satisfaction with the Peristeen cone catheter.

4. Investigational device and comparator(s)

4.1. Description of investigational device

The Peristeen transanal irrigation system is a manual system consisting of a control unit (featuring a pneumatic bulb pump and a four-position rotary switch), a water bag (featuring a pressure relief valve), a lubricated cone catheter, tubes and connectors. The system is also accompanied by straps to secure the system on the thigh while being used, if needed, and a toilet bag to store the system in when not in use. Peristeen is a non-sterile product classified as class I device according to the Medical Device Directive, MDD 93/42/EEC and is CE-marked.

4.7. Comparator

The comparator in this investigation is current standard of care for patients with LARS which is conservative bowel management. This is defined as supportive therapy according to the individual treatment protocols available at each participating site.

For LARS patients these protocols consist of:

- Dietary modifications (bulk forming)
- Biofeedback-assisted pelvic floor training
- Abdominal massage
- Treatment with loperamide, oral laxative and suppositories
- Digital rectal stimulation
- Small volume enemas (< 150 ml)

5. Design of the clinical investigation

5.1. General

This investigation is a randomised, open-label, comparative, parallel, post market study. In total, 34 rectal resection subjects with major LARS will be included and randomised, and each subject will have an inclusion visit and two test visits and follow-up phone calls in between. Each subject will be enrolled for a study duration of 12 weeks. Subjects will be randomized to the treatments stratified by neo-adjuvant radiotherapy. Training will be performed at the randomisation visit V1. If needed, patients may have additional training sessions before being able to perform the irrigation on their own. After the training sessions the study duration is 12 weeks.

[figure not shown]

Figure 1 Design of the randomised clinical study

5.2. Primary endpoint

- LARS score, obtained from the LARS score questionnaire* (6)

5.3. Secondary endpoints

- Number of subjects with Major LARS*
- FIQL Score – scale 1, Modified American Society for Colorectal Surgeons Questionnaire* (7)

5.7. Randomisation Procedure

As this is a parallel investigation, subjects are assigned to one treatment in a 1:1 allocation ratio, where each subject will be randomized into one of two treatment arms i.e. investigational device and comparator.

At visit 1 investigator or his representative, as per the randomisation list, allocates a randomisation treatment code to each patient. The randomisation code is recorded in the electronic Case Report Form (eCRF) by investigator or his representative.

5.8. Blinding

Subjects will not be blinded in this investigation due to self-management of the investigational device. Furthermore, site personnel i.e. nurses and/or assisting Coloplast personnel are also not blinded. Coloplast personnel not on-site or involved in trial conduct i.e. the statistician will be blinded until the time of data base lock.

As this is a parallel study, subjects will be assigned one treatment only and randomly assigned a treatment in a 1:1 allocation ratio for the duration of the study.

5.9. Total expected duration of the clinical investigation

The dates below are approximate, and no subjects will be enrolled before all required approvals have been obtained. If changes are required, applicable EC and regulatory authorities will be notified.

Activity	Estimated time
First subject enrolled	SEP 2020
Last subject enrolled	FEB 2021
Last subject completed	MAY 2021
Final Report	AUG 2021

6. Clinical Investigation population

The clinical investigation will be conducted in 34 subjects enrolled in 4-8 clinical investigation sites.

Patients who have undergone rectal resection for rectal cancer (with or without pouch construction) and have major LARS defined as LARS score ≥ 30 .

6.1. Eligibility criteria

To be included in the investigation, the subjects must comply with the selection criteria described below.

6.1.1. Inclusion criteria

Table 1 Inclusion criteria and justification hereof:

Inclusion criteria To be included the subjects must:	Justification To ensure that:
1. Be at least 18 years of age and have full legal Capacity	To ensure voluntarily and that the Helsinki declaration is met
2. Have given written informed consent	To meet the Helsinki declaration

6.1.3. Pregnancy

For female subjects with childbearing potential (they have had at least one period during the last 12 months), a urine pregnancy test will be performed at the inclusion visit, to ensure the subject is not pregnant. The urine pregnancy test will be performed by dipstick at the trial site. Furthermore, the female patients with childbearing potential should use safe contraceptives during study duration.

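### Section 6.1.3 defines childbearing potential only by a period in the last 12 months, so a woman who may still be fertile but has no periods for another reason is not tested for pregnancy

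*Combined protocol and SAP*

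**What the plan says.** Section 6.1.3 explains the term in a bracket when it prescribes, for "female subjects with childbearing potential (they have had at least one period during the last 12 months), a urine pregnancy test". It attaches two safeguards to that term. The first is the test and its reason: "a urine pregnancy test will be performed at the inclusion visit, to ensure the subject is not pregnant". The second is contraception: "the female patients with childbearing potential should use safe contraceptives during study duration". The test is a dipstick done at the trial site.

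The population is set elsewhere. The inclusion table in section 6.1.1 requires subjects to "Be at least 18 years of age and have full legal Capacity", and the visible text gives no upper age limit. Section 6 describes the subjects: "Patients who have undergone rectal resection for rectal cancer". Section 5.1 adds: "Subjects will be randomized to the treatments stratified by neo-adjuvant radiotherapy". The same section gives the period over which the contraception sentence applies: "Each subject will be enrolled for a study duration of 12 weeks".

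**The concern.** The bracket uses bleeding as a stand-in for fertility. That works where periods have stopped because of menopause or sterility. It does not work where they are absent for another reason and fertility may remain. A site that follows section 6.1.3 exactly would be right to skip the test for such a woman, so the gap lies in the rule and not in how sites apply it.

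The trial population makes the case foreseeable. Adults may enter from age 18, all have had surgery for rectal cancer, and the stratification factor shows that some are expected to have had radiotherapy. What is at stake is a safety check at entry. No endpoint, power figure or analysis depends on it.

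**Working it through.** The plan gives no figure to reproduce here, so the check applies the bracket literally to four kinds of woman. That periods can stop because of hormonal contraception or cancer treatment is taken as general medical knowledge and is not stated in the documents.

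| Woman at the inclusion visit | Meets the bracket? | Tested? | Contraception sentence applies? | Practical gap |
|---|---|---|---|---|
| At least one period in 12 months | Yes | Yes | Yes | None |
| No period; postmenopausal or sterile | No | No | No | None |
| No period because of hormonal contraception | No | No | No | Missed test; no requirement to continue |
| No period after cancer treatment; may still be fertile | No | No | No | Missed test; no contraception requirement |

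The rule works as intended in the first two rows. In the last two it falls short of the section's stated reason for testing.

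The next question is whether anything else closes the gap.

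- The visible text has no second definition of the term, no age, menopausal or surgical criterion, and no exception for periods absent for another cause.
- The visible task lists for the follow-up calls and the termination visit V2 contain no pregnancy check. On that text, a woman left out at inclusion stays left out for the 12 weeks.

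On size, the documents give no number of women, no age distribution and no rate of treatment-related loss of periods. Assumed shares can show only the order of magnitude. Suppose 40% to 50% of subjects are women, 10% to 20% of those are premenopausal, and 25% to 50% of those have no periods for another cause:

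- Low end: 34 × 0.40 × 0.10 × 0.25 = 0.34 women.
- High end: 34 × 0.50 × 0.20 × 0.50 = 1.7 women.
- With 1:1 allocation (section 5.7), half would be assigned to irrigation: 0.34 / 2 = 0.17 to 1.7 / 2 = 0.85.

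Every share is an assumption. The result counts women outside the definition, not pregnancies. A count of pregnancies would also need the chance of an unrecognised pregnancy, which the documents do not give.

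**The case against.** The strongest reply is that the rule is stated once, applied consistently and drawn fairly wide. A single period in a whole year is enough, so women with irregular or recently stopped periods are still tested. A woman whose periods stopped because of contraception already does what the contraception sentence asks. Both gaps matter in practice only for women without periods after treatment who remain fertile, and nothing in the documents shows that any would be enrolled. The device is CE-marked and class I (section 4.1).

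Most of this stands and limits the point. It does not remove it: the missed test remains for both groups, against a purpose that the section itself states.

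A second reply is that exclusion criteria 1 to 8 and part of the inclusion table are not in the available text. A pregnancy exclusion for all women may be there, and its absence from this copy is not a fault of the plan. Such an exclusion could mean that every woman is asked about pregnancy. It would not by itself extend the dipstick test or the contraception sentence to the women in question.

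Two stronger readings are tempting and should not be adopted.

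- A reader might infer from section 18.4, which lists fetal distress, fetal death and congenital abnormality, that the plan regards irrigation as a fetal hazard. That section is a general definition of seriousness. The event-rate rows shown shortly before section 18.3 name cramps, mucosal tear, fissure, rectal bleeding and bowel perforation. No fetal event is among them, although the table may be incomplete.
- A reader might say that the rule defeats itself, because contraception can take a woman outside a rule that asks for contraception. That is true only formally, since she is already using it.

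**Conclusion.** The point holds as a minor gap in wording. Section 6.1.3 ties both safeguards to one criterion, and that criterion leaves out women who may still be fertile but have had no period in 12 months. For them the section does not meet its own purpose.

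The number of such women among the 34 subjects cannot be estimated from the documents and is probably very small. The illustrative shares are not evidence of a count. The documents do not support a claim that a pregnant subject is likely to be randomised, or that the device poses a fetal risk. The primary result is unaffected.

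The conclusion rests on a literal reading of the bracket and on the visible text having no other rule that would bring these women under the test or the contraception sentence.

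**What to change.** The sponsor should reconcile the bracket in section 6.1.3 with the purpose stated there, so that absence of periods alone does not exempt a woman who may still be fertile. The section should also state whom the test covers and whom the contraception sentence covers, including whether women already using contraception are expected to continue. The exact clinical wording is for the sponsor and the investigators to settle.

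The cost is one clause and possibly a few more tests with the dipstick already planned at the sites. The change adds no visit, endpoint or analysis and leaves the sample size as it is.

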6.2. Recruitment and enrolment

Recruitment of potential subjects will begin once all regulatory requirements have been fulfilled. The recruitment time is estimate to approximately 6 months.

Recruitment method	Coloplast Database
Potential subjects	Recruitment will go through the Investigators own patient database Potential subjects are identified by the following searching criteria: 
• Have a LARS score ≥ 30 after rectal resection• Patients must be evaluated to be suitable for transanal Irrigation procedure with a cone catheter by endoscopy, defecography or comparable procedure• Be at least 18 years of age
First contact	The identified potential subjects will as first contact be sent an Invitation and Reply Letter by mail or email. If a potential subject does not return the reply letter or answer the email, they may be contacted by phone, mail or email to make sure that they have received the approach.
Second contact	If potential subjects return the Reply Letter/reply to the email or have called the investigator as first contact and are interested, the Investigator or delegated site personnel will contact the subjects by phone and give a short introduction to the investigation and go over the inclusion and exclusion criteria. If the subjects do not meet the inclusion criteria or meet the exclusion criteria, this will be registered in the Subject Screening Log.
Subject Information Form	If subjects are eligible and interested in participating, then written information about the investigation (subject information) will be sent to the subjects to ensure that they are given the opportunity to read about the investigation before a possible informational visit, and so that they can prepare any possible questions they may have. Information visit V0 will be booked at this point and the subjects are instructed to contact the investigator or delegated study personnel if they, after having read the subject information, no longer are interested in participation in the study.
First visit Information visit	If an eligible subject is interested in participating, baseline visit (V0) will be arranged. When arranging the visit, it will be ensured, that the subject has received the Subject Information prior to the visit. The subjects will receive both written and verbal information about the possibility of bringing a companion to the informational visit and to any possible subsequent visits. See section 16. for information to be given to the subjects, as well as the informed consent process.
Enrolment and Baseline visit (V0)	The subjects will be offered at least 24 hours to think about if they will participate, or if they wish to give consent right away. If/when the subject decides to participate, he/she will be asked to sign the relevant forms (see section 16). If a subject so desires, and it is certain that it is understood what the investigation entails, and the relevant forms have been signed the subjects are considered enrolled in the investigation.

- Instruct subject in completing subject diaries
- Instruct subject in use of the investigational devices/standard of care
- Instruct and remind the subject to follow the study specific procedures between visits
- Schedule next visit in 12 weeks

Phone call (twice a week for the first 3 weeks; 6 phone calls, 30 mins):

- Give support in the use of the investigational device/standard of care
- Remind the subject to complete diaries
- Complete eCRF
- Registration of AEs/ADEs/SAEs/SADEs
- Remind the subject to follow the study specific procedures between visits

Termination visit (V2) after 12 weeks (\pm 4 days):

- Complete eCRF
- Complete QoL questionnaires
- Registration of AEs/ADEs/SAEs/SADEs
- Review AEs/ADEs/SAEs/SADEs
- Collect subject diaries
- Collect investigational device
- Fill in termination form

Assessment(s)						
On-site visit • LARS score Questionnaire • FIQL score Questionnaire • EQ – 5D – 5L • Satisfaction with treatment • [REDACTED]	Subject/Investigator (All)		X			X
On-site visit • [REDACTED] • [REDACTED]	Subject/Investigator (Peristeen Cone only)					X
Subject diary: • [REDACTED] • [REDACTED] • [REDACTED]	Subject (All) Run-in period (14 days from Visit 1)		X	X		
Subject diary: • [REDACTED]	Subject (Peristeen Cone only)			X		
Device training	Investigator		X			
AE/SAE reporting			X		X	X
Registration of termination						
Termination form	Investigator					X

7.3. Case Report Forms

All assessments and observations throughout the investigation for each subject must be carefully recorded in an electronic CRF (eCRF) on a PC provided to the site by Coloplast.

CRFs will be filled in by the investigator and/or delegated site personal, who have signed the Site Personnel Signature and Delegation List and Clinical Investigation Training Log. As eCRFs are used delegated site personal will be required to complete e-learning prior to system access. Delegated personal will receive credentials.

Lars score, [REDACTED] questionnaire (FIQL and EQ-5D) will be filled out by subjects using paper CRF and entered into the eCRF afterwards.

For the purpose of this clinical investigation the below described monitoring procedures have been determined.

9.1.1. Site selection visit

Depending on the prospective clinical investigation sites experience with the specific investigational device, a qualification or site selection visit shall be performed during which the feasibility of the clinical investigation requirements will be discussed and common agreement between sponsor and principal investigator shall be reached. This visit may also be replaced by one or more phone calls if the principal investigator is known to the sponsor, or if it is not at all feasible to perform a Site selection visit on-site.

